15.1 DLT (Primary Endpoint)

Population: DE analysis set

The DLT information will be based on "Adverse Events" eCRF page with "Is the adverse event a dose limiting toxicity?" = Yes or with "Is the adverse event a dose limiting toxicity upon SMC review" = Yes.

A summary table of DLTs during the DLT period will be provided for each dose level and overall with:

- Number of participants with at least one DLT as per SMC decision

The listing of DLTs will also be provided.

15.2 Adverse Events

Definitions

Treatment-emergent adverse events: those events with onset dates occurring within the on treatment period.

Counting rules and observation periods for AEs during the on treatment period (TEAEs):

- If an AE is reported for a given subject more than once during treatment, the worst severity and the worst relationship to trial treatment will be tabulated.

- Adverse events related to trial treatment are those events with relationship missing, unknown or related to at least one treatment (peposertib, RT or capecitabine).
- Adverse events related to peposertib are those events related to peposertib, regardless of relationship with RT and/or capecitabine
- Adverse events related to RT are those events related to RT, regardless of relationship with peposertib and/or capecitabine
- Adverse events related to capecitabine are those events related to capecitabine, regardless of relationship with peposertib and/or RT
- In case a subject has events with missing and non-missing grades, the maximum of the non-missing grades will be displayed.

For identification of AE treatment emergence, incomplete dates will be handled using the rules presented in Section 0.

Adverse events will be summarized by worst severity (according to NCI-CTCAE version 5.0) per participant, using the latest version of MedDRA preferred term (PT) as event category and MedDRA primary system organ class (SOC) body term as Body System category.

Missing data handling

Incomplete AE-related dates will be handled using the rules presented in Section 0. In case a participant has events with missing and non-missing grades, the maximum of the non-missing grades will be displayed. No imputation of missing grades will be performed.

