6.6.1 Definition of Dose Limiting Toxicity

A DLT is defined as any of the following TEAEs considered possibly related to peposertib and/or capecitabine and/or RT by the Investigator and/or the Sponsor up to completion of the assigned CRT treatment (25 FD or 28 FD) (DLT period). A DLT must be confirmed by the SMC:

1. An adverse drug reaction that, in the opinion of the SMC, is of potential clinical significance such that further dose escalation would expose participants to unacceptable risk
2. Any occurrence of drug-induced liver injury (DILI) meeting the Hy's law criteria (i.e. defined as aminotransferases $> 3 \times$ ULN, alkaline phosphatase $< 2 \times$ ULN, total bilirubin $\geq 2 \times$ ULN, with no other reason to account for these abnormalities)
3. Any Grade 3 toxicity, excluding:
 - a) Diarrhea (< 7 days duration) despite early, adequate and optimal antidiarrhea therapy
 - b) Neutropenia lasting for ≤ 5 days and not associated with fever

- c) Isolated Grade 3 lymphocytopenia without clinical correlate
 - d) Grade 3 radiation dermatitis that resolves to Grade ≤ 2 with supportive measures within 5 weeks
 - e) Nausea and vomiting (< 3 days duration) with adequate and optimal therapy
 - f) Fatigue or headache (< 7 days duration) following initiation of adequate supportive care
 - g) Any other single laboratory values out of the normal range that have no clinical significance as confirmed by the Investigator, and that resolve to Grade 2 or less with adequate measures within 7 days
 - h) Grade 3 thrombocytopenia without bleeding
4. All Grade ≥ 4 AEs at least possibly related to study intervention, irrespective of duration, excluding:
- a) Isolated Grade 4 lymphocytopenia without clinical symptoms
 - b) Neutropenia lasting for ≤ 5 days and not associated with fever
5. Any toxicity related to study intervention that causes the participant to receive less than 80% of the planned peposertib, capecitabine or RT dose

[figure not shown]

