8.3 Adverse Events and Serious Adverse Events

The definitions of an AE and a serious adverse event (SAE) are in [Appendix 7](#).

8.3.1 Time Period and Frequency for Collecting Adverse Event and Serious Adverse Event Information

The AE reporting period for safety surveillance begins when the participant is initially included in the study (date of first signature of informed consent/date of first signature of first informed consent) and continues until the final assessment at 1 year. Any AE assessed as not related to study intervention will be recorded only up to the short-term safety follow-up period. Any AE assessed as related to study intervention will be recorded up to resolution or permanent outcome, irrespective of the time elapsed since the last administration of study intervention.

Any SAE assessed as related to study intervention must be recorded and reported, as indicated in [Appendix 7](#), whenever it occurs, irrespective of the time elapsed since the last administration of study intervention. Any SAE assessed as not related to study intervention must be recorded and reported, as indicated in [Appendix 7](#), only up to Week 27 in the long-term safety follow-up period.

The method of recording, evaluating, and assessing causality of AEs (including SAEs) and the procedures for completing and transmitting SAE reports are in [Appendix 7](#).

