9.4.2 Safety Analyses

Statistical analysis methods for safety endpoints are described in [Table 13](#).

Table 13 Statistical Analysis Methods for Safety Endpoints

Endpoint	Statistical Analysis Methods
Primary	
Occurrence of DLTs	The number and proportion of participants experiencing a DLT confirmed by the SMC during the DLT period will be reported by dose level. Analysis will be based on the DE Analysis Set.
Secondary	
Occurrence of TEAEs and treatment-related AEs according to the CTCAE version 5.0	All AEs will be coded according to the MedDRA, version 21.0 or higher. The severity of AEs will be graded using NCI-CTCAE v5.0 toxicity grades. Adverse events related to study intervention will be defined as any AE considered related to any study intervention. In addition, missing classifications concerning study intervention relationships will be considered related to the study intervention(s). Adverse events observed from the first dose until 30 days after last study intervention administration (i.e. TEAEs) will be summarized according to MedDRA system organ classes and preferred terms. The incidence and type of the following will be analyzed: 
 • TEAEs and SAEs • TEAEs and SAEs related to study intervention • TEAEs with NCI-CTCAE Grades ≥ 3 • TEAEs related to study intervention with NCI-CTCAE Grades ≥ 3 • AEs leading to withdrawal, dose modifications, or permanent study intervention discontinuation • Deaths and reasons for death will be tabulated. In addition, deaths within 30 days from last dose administration and deaths beyond this period up to 90 days follow-up and reasons for death will be tabulated. Analyses will be based on the Safety Analysis Set.

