Percent change from baseline: $100 * (visit value - baseline value) / baseline value$

Definition of on treatment period:

On treatment period is defined as the time from the first administration of study intervention to the last administration of study treatment + 30 days, or the clinical cut-off date (if the treatment is still ongoing), or death, whichever occurs first.

Date of last known to be alive

The date of last known to be alive will be derived for participants not known to be dead at the analysis cut-off using the latest complete date among the following:

- All subject assessment dates:

- Laboratory assessments using information from “Hematology”, “Biochemistry”, “Coagulation”, “Urinalysis”, “Pregnancy test” and “Creatinine Clearance” eCRF pages (LBDTC variable from LB SDTM domain to be used)
- Vital signs using information from “Vital signs” eCRF page (VSDTC variable from VS SDTM domain to be used)
- Performance status using “ECOG Performance status” eCRF page (QSDTC variable from QS SDTM domain to be used)
- ECG, using information from both local and central ECGS (EGDTC variable from EG SDTM domain to be used)
- Tumor assessments using “Tumor assessments” eCRF pages (TRDTC/TUDTC variable from TR/TU SDTM domain to be used)
- Surgery information using “Rectal Surgery at week 15”, “Rectal Surgery after Week 15”, “Surgery after discontinuation” eCRF pages
- Anti-cancer treatment after discontinuation start and end date from “Anti-Cancer treatment after discontinuation” eCRF page.
- Start dates of concomitant medications or anti-cancer therapies administered after study treatment termination using “Concomitant medications”, “Anti-cancer treatment after discontinuation details” eCRF pages (CMSTDTC variable from CM SDTM domain to be used)
- AE start dates from “Adverse events details” eCRF page (AESTDTC variable from AE SDTM domain to be used)
- Study treatment administration dates using “M3814 (PEPOSERTIB)/PLACEBO Administration Details”, “RT Administration” and “Capecitabine Administration” eCRF pages (EXSTDTC variable from EX SDTM domain to be used)
- Last known to be alive date using “Survival Follow-up page” (SSDTC variable from SS SDTM domain where SSCAT=“SURVIVAL FOLLOW-UP”), where status is “Alive”.

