15.2.1 All Adverse Events

Population: SAF Analysis Set

Adverse events will be summarized by worst severity (according to NCI-CTCAE version 5.0) per subject, using the most recent available MedDRA version (21.1 or higher) PT as event category and primary SOC body term as Body System category.

Frequency tables for AEs captured on the “Adverse Events” eCRF pages will be based on TEAEs as defined above.

A first overview table of adverse events will be provided by dose level and overall by summarizing the number and percentage of participants with any:

- TEAE
- TEAEs related to trial treatment, (i.e. peposertib, RT, or capecitabine)

- TEAEs related to peposertib
- TEAEs related to RT
- TEAEs related to capecitabine
- Serious TEAE
- Serious TEAE related to trial treatment (i.e. peposertib, RT, or capecitabine)
- Serious TEAEs related to peposertib
- Serious TEAEs related to RT
- Serious TEAEs related to capecitabine
- TEAEs with grade ≥ 3
- TEAEs with grade ≥ 4
- TEAEs with grade ≥ 3 related to trial treatment (i.e. peposertib, RT or capecitabine)
- TEAEs with grade ≥ 4 related to trial treatment (i.e. peposertib, RT or capecitabine)
- TEAEs with grade ≥ 3 related to peposertib
- TEAEs with grade ≥ 4 related to peposertib
- TEAEs with grade ≥ 3 related to RT
- TEAEs with grade ≥ 4 related to RT
- TEAEs with grade ≥ 3 related to capecitabine
- TEAEs with grade ≥ 4 related to capecitabine
- TEAEs leading to dose modification of any trial treatment (i.e. peposertib, RT or capecitabine)
- TEAEs leading to dose modification of peposertib
- TEAEs leading to dose modification of RT
- TEAEs leading to dose modification of capecitabine
- TEAE leading to death
- TEAE leading to death related to trial treatment, peposertib, RT or capecitabine
- TEAE leading to death related to peposertib
- TEAE leading to death related to RT
- TEAE leading to death related to capecitabine
- TEAE leading to trial discontinuation

- TEAE leading to temporary discontinuation of at least one trial treatment
- TEAE leading to temporary discontinuation of all trial treatments
- TEAE leading to temporary discontinuation of M3814
- TEAE leading to temporary discontinuation of RT
- TEAE leading to temporary discontinuation of Capecitabine
- TEAE leading to permanent discontinuation of at least one trial treatment
- TEAE leading to permanent discontinuation of all trial treatments
- TEAE leading to permanent discontinuation of M3814
- TEAE leading to permanent discontinuation of RT

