- TEAE leading to permanent discontinuation of Capecitabine

Frequency tables summarizing events in the following categories will be prepared by dose level and overall, sorted by alphabetical order of SOC and PT:

- TEAEs
- TEAEs related to trial treatment (i.e. peposertib, RT, or capecitabine)
- TEAEs related to peposertib
- TEAEs related to RT
- TEAEs related to capecitabine
- Serious TEAEs
- TEAEs excluding SAEs, with overall frequency $\geq 5\%$ by SOC and PT (threshold will be applied on PT)
- Serious TEAEs related to trial treatment
- Serious TEAEs related to peposertib
- TEAEs by worst CTCAE grade: any grade (including AEs with missing grade), grades ≥ 3 , ≥ 4 and 5
- TEAEs related to trial treatment by worst CTCAE grades: any grade (including AEs with missing grade), grades ≥ 3 , ≥ 4 and 5
- TEAEs related to peposertib by worst CTCAE grades: any grade (including AEs with missing grade), grades ≥ 3 , ≥ 4 and 5
- TEAEs related to RT by worst CTCAE grades: any grade (including AEs with missing grade), grades ≥ 3 , ≥ 4 and 5

- TEAE related to capecitabine by worst CTCAE grades: any grade (including AEs with missing grade), grades ≥ 3 , ≥ 4 and 5
- TEAEs leading to death

In addition, all TEAEs and TEAEs related to peposertib with at least 2 participants will be summarized in two tables sorted by frequency (descending order) and PT.

The following listings will be produced based on the “Adverse Events” eCRF page:

- All AEs (whether treatment-emergent or not)
- Serious TEAEs related to any trial treatment
- TEAEs within 6 weeks after surgery and delayed surgery

These listings will include the following items:

- Dose level
- Subject identification number
- Age
- Sex
- Race
- First and last dose date for peposertib, RT and capecitabine
- Reported Term with SOC and PT
- Start, change and end date with their corresponding treatment day
- Treatment Emergent Adverse Events flag (N/Y; only for the listing of all AEs)
- Timing related to treatment (if same day of treatment administration)
- TEAE related to peposertib flag (N/Y)
- TEAE related to RT flag (N/Y)
- TEAE related to capecitabine flag (N/Y)
- Serious Adverse Events flag (N/Y; only for the listing of all AEs)
- DLT flag (Y/N)
- CTCAE Grade
- Action taken with peposertib, with RT and with capecitabine
- Outcome of AE
- AE occurred after COVID-19 pandemic start (Y/N).

Evaluation of COVID-19 effects on AEs

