15.2.3 Late Toxicities

A number of outputs will be produced for late adverse events. An adverse event is defined as a late toxicity if it starts after the on-treatment period, and it meets one of the following criteria:

- It is the first occurrence of adverse event for this participant on MedDRA preferred term level
- It is a recurring adverse event but there is gap between the end date of the previous occurrence and the start date of the re-occurrence (start date of re-occurrence – end date of previous occurrence > 0)
- It is a recurring adverse event and there is no gap between the end date of the previous occurrence and the start date of the re-occurrence, and the grade has worsened.

The following outputs will be produced for late toxicities:

- Table of all late toxicities by worst CTCAE grades: any grade (including AEs with missing grade), grades ≥ 3 , ≥ 4 and 5
- Listing of all late toxicities related to any trial treatment
- Listing of all late toxicities grade ≥ 3

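### The SAP defines a treatment-emergent AE by onset date alone, so an AE that starts before first dose and worsens on treatment can drop out of the TEAE tables, depending on a recording convention the documents do not state

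*SAP*

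**What the plan says.** **TEAE definition.** SAP Section 15.2 gives "Treatment-emergent adverse events: those events with onset dates occurring within the on treatment period". SAP Section 9 sets the window: "On treatment period is defined as the time from the first administration of study intervention to the last administration of study treatment + 30 days", cut short by the clinical cut-off or death. The Section 9 rules for incomplete AE dates also test emergence on the onset date only.

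**Protocol wording.** Protocol Section 9.4.2, Table 13, says: "Adverse events observed from the first dose until 30 days after last study intervention administration (i.e. TEAEs) will be summarized". SAP Section 7, which lists changes from the protocol's planned analyses, does not mention the TEAE definition.

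**Collection.** Under Protocol Section 8.3.1 the AE reporting period "begins when the participant is initially included in the study", which that sentence ties to the consent signature. Protocol Table 1 has an AE assessment in screening, Day -28 to -1.

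**Use.** SAP Section 15.2.1 says the frequency tables for AEs captured on the AE "eCRF pages will be based on TEAEs as defined above". The interruption and withdrawal tables in Section 15.2.2 are TEAE tables too.

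**Recording of grade changes.** The AE listings in SAP Section 15.2.1 carry "Start, change and end date with their corresponding treatment day". The late-toxicity rule in Section 15.2.3 includes a re-occurrence that follows the previous one without a gap "and the grade has worsened". Protocol Appendix 7 leaves recording detail to the sponsor's CRF completion conventions, which are not among the documents.

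**DLTs.** Protocol Section 6.6.1 begins "A DLT is defined as any of the following TEAEs". SAP Section 15.1 identifies DLTs from two eCRF items and counts participants by SMC decision.

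**The concern.** Worsening of an existing complaint under treatment is a toxicity signal that a dose-escalation trial needs to see. Participants may enter after oxaliplatin-based induction chemotherapy (Protocol Section 5.1), so symptoms around the time of consent are plausible. Under an onset-only rule, an AE that starts at Grade 1 between consent and first dose and reaches Grade 3 during chemoradiation may never be classed as treatment-emergent.

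Occurrence of TEAEs is a secondary endpoint. The tables by dose level rest on planned cohorts of 3, where one participant moves a rate a long way. An endpoint definition that is narrower than the protocol's, and not declared as such, should not depend on a data-entry convention that the plan does not state.

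**Working it through.** There is no stated figure to reproduce; this is a check of definitions.

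**Step 1. Compare the two definitions.** Take AE *A*: Grade 1 onset between consent and first dose, Grade 3 during chemoradiation.

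- Protocol Table 13 asks whether the AE was observed in the window. The Grade 3 episode was, so on a natural reading *A* counts.
- SAP 15.2 asks whether the onset date lies in the window. The result depends on what the database holds as the onset of the Grade 3 episode.

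**Step 2. Apply both recording conventions.** Take also AE *B*: Grade 1 onset on treatment, worsening more than 30 days after the last dose.

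| AE | Grade change kept in one record | Grade change opens a new record |
|---|---|---|
| *A* | Start date is before first dose, so not a TEAE | New start date is on treatment, so a Grade 3 TEAE |
| *B* | TEAE; may be tabulated at its later, worse grade | Grade 1 TEAE, plus a late toxicity under 15.2.3 |

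The separate change date in the listing fits the first column. The contiguous re-occurrence in 15.2.3, with its own start date and a worse grade, fits the second. Neither settles the matter.

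**Step 3. Trace AE *A* under the one-record convention.**

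- TEAE frequency, Grade ≥3 and treatment-related tables (15.2.1): absent.
- Interruption and withdrawal tables (15.2.2): absent, even if *A* led to withdrawal.
- Late toxicities (15.2.3): absent, because the event must start after the on-treatment period.
- All-AE listing (15.2.1): present, flagged as not treatment-emergent.
- SAE summary (15.3.2): worded without a TEAE restriction, so *A* would appear there if serious.
- Laboratory shift tables (15.4): baseline to worst on-treatment grade, so CTC-gradable laboratory worsening is shown; clinical symptoms are not.

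**Step 4. Check the DLT path.** SAP 15.1 uses the eCRF DLT items and the SMC decision, with no filter on the derived TEAE flag. If *A* is confirmed as a DLT, it is counted. It could still be missing from the Grade ≥3 TEAE table at the same dose level, which would sit badly with Protocol 6.6.1, where every DLT is a TEAE.

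**Step 5. Size, as illustration only.** If one participant's only Grade ≥3 event is missed, the rate falls by 1/n.

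- n = 3 (planned cohort size, Protocol 9.2): 1/3 = 33.3 percentage points.
- n = 19 (treated as of 06 May 2021, Protocol 1.1): 1/19 = 5.3 percentage points.

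These figures hold for any single miscounted participant. They are not an estimate of how often this would happen.

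**The case against.** The strongest reply is that the rule may already work. Section 15.2.3 provides for a worsening that has its own start date. If the database is built that way, AE *A* is a TEAE and AE *B* a late toxicity, with nothing to correct. This stands as a possibility, and it makes the concern conditional.

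The group at risk is also smaller than it first looks. Protocol Appendix 7 treats conditions already present at the initial visit as baseline conditions unless they worsen. Many tumor or post-induction symptoms would therefore become AEs only on worsening. What remains is mainly AEs that newly arise between consent and first dose. This stands too.

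Nor would the event vanish: the all-AE listing, the SAE summary and the laboratory shift tables offset part of the loss, and with 19 treated participants a listing can be read in full. No dose decision still depends on these tables, since all participants have completed treatment and Phase II will not start. That lowers the stakes. It does not make the Grade ≥3 and discontinuation tables right.

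Two stronger readings are tempting and should be resisted.

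- A reader might join the SAP's TEAE rule to Protocol 6.6.1 and infer that such an AE cannot be a DLT. The documents do not support this. The protocol's own TEAE wording does not turn on onset date, and SAP 15.1 applies no TEAE filter.
- A reader might infer that 15.2.3 contradicts 15.2 because it mentions worsening. It does not. A late toxicity must itself start after the on-treatment period, so that rule is onset-based as well.

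**Conclusion.** The concern holds in conditional form. SAP 15.2 is narrower than Protocol Table 13, and SAP Section 7 does not declare the difference. If grade changes are kept within one record, clinical AEs that start between consent and first dose and worsen on treatment are under-counted in the TEAE frequency, Grade ≥3 and discontinuation tables. If each grade change opens a new record, they are not.

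The conclusion assumes that such AEs occur, which is plausible but not quantified in the documents, and that a worsening can keep its original onset date, which the documents leave open. The 33.3- and 5.3-point figures only show how sensitive small denominators are. The primary endpoint count is unaffected. Severity is minor to moderate.

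**What to change.** In SAP Section 15.2, define a TEAE as an AE that meets either condition:

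1. onset within the on-treatment period; or
2. onset before first dose, with an increase in CTCAE grade or becoming serious within the on-treatment period, dated by the change date or by the start date of a new record.

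Tabulate the worst grade reached within that period, so that a worsening after day 30 is not reported as on-treatment toxicity. State in the SAP how grade changes are recorded. Align the wording with Protocol Table 13 and with the use of TEAE in Protocol Section 6.6.1, so that any SMC-confirmed DLT also appears in the TEAE tables. If the narrower rule is kept on purpose, list it in SAP Section 7.

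The cost is one or two sentences and a small change to the AE derivation. TEAE rates may rise slightly. If the convention proves to be one record per grade change, a confirming sentence, with the alignment above, closes most of the gap.

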5.4 Screen Failures

Individuals who do not meet the criteria for participation in this study (potential participants who failed screening) may be rescreened. Rescreened participants will be assigned a new participant number. Retesting before baseline will be permitted only once, and the test for the specific abnormal value must be repeated within the timeframe of the Screening period. The last value of the previously questioned test result must meet the study criteria before start of study intervention. In the case of a rescreen and the screening CT scan is > 28 days from the previous screening scan, the screening CT must be repeated.

6 Study Intervention(s)

Study intervention is any investigational intervention(s), marketed product(s), placebo, or medical device(s) intended to be administered to a study participant per the study protocol. For this study, peposertib is the investigational intervention, and the study interventions include peposertib, capecitabine, and RT. Peposertib and capecitabine will be administered on an outpatient basis, except on dosing days requiring predose PK samples (Table 4, Table 7).

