Only dates associated with actual examinations of the participant reported in the eCRF will be used in the derivation. Dates associated with a technical operation unrelated to participant status (such as the date a blood sample was processed) will not be used. Assessment dates after the cut-off date will not be considered for derivation of last date known to be alive.

Definition of duration/ time since an event

Duration will be calculated by the difference of start and stop date + 1 (e.g., survival time [days] = date of death – date of Study day 1 + 1), if not otherwise specified.

The time since an event (e.g. time since first diagnosis) will be calculated as date of event – Study day 1 + 1.

Conversion factors

The following conversion factors will be used to convert days into months or years: 1 month = 30.4375 days, 1 year = 365.25 days.

Handling of missing data

Unless otherwise specified, missing data will not be replaced.

In all participant data listings imputed values will be presented, and the imputed information will be flagged (if not specified otherwise).

Missing statistics, e.g., when they cannot be calculated, should be presented as “nd” (not done). For example, if n=1, the measure of variability (Sd) cannot be computed and should be presented as “nd”.

Adverse events

For identification of AE treatment emergence, incomplete dates will be handled as follows:

- In case the onset date is completely missing, or the onset is in the same year (if the onset year is available only) or the onset is in the same month and year (if the day is missing) as start of trial treatment then the onset date will be replaced either by the start of trial treatment date or the AE resolution date, whichever is the earliest.
- In all other cases, the missing onset day or onset month will be replaced by 1.
- Incomplete stop dates will be replaced by the last day of the month (if day is missing only), if not resulting in a date later than the date of subject’s death. In the latter case, the date of death will be used to impute the incomplete stop date.
- In all other cases, the incomplete stop date will not be imputed.

Previous/Concomitant medication

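### The SAP counts missing causality as related only in the pooled trial-treatment category, so such events can drop out of the peposertib, RT and capecitabine tables

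*SAP*

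**What the plan says.** Protocol Section 9.4.2 (Table 13) first gives an aggregate definition: "Adverse events related to study intervention will be defined as any AE considered related to any study intervention". It then adds that "missing classifications concerning study intervention relationships will be considered related to the study intervention(s". The introduction to protocol Section 6 states that "the study interventions include peposertib, capecitabine, and RT".

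SAP 15.2 (counting rules) has one pooled definition and three component definitions:

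- Pooled: "Adverse events related to trial treatment are those events with relationship missing, unknown or related to at least one treatment (peposertib, RT or capecitabine".
- Peposertib: "Adverse events related to peposertib are those events related to peposertib, regardless of relationship with RT and/or capecitabine".
- RT: "Adverse events related to RT are those events related to RT, regardless of relationship with peposertib and/or capecitabine".
- Capecitabine: "Adverse events related to capecitabine are those events related to capecitabine, regardless of relationship with peposertib and/or RT".

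Only the pooled definition mentions missing or unknown. The general rule in SAP Section 9, under the handling of missing data, is: "Unless otherwise specified, missing data will not be replaced".

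SAP 15.2.1 then plans peposertib-related rows or tables for all treatment-emergent events, serious events, Grade 3 or higher, Grade 4 or higher and fatal events, plus a table of peposertib-related preferred terms seen in at least 2 participants. SAP Section 7, which lists changes from the protocol's planned analyses, does not mention causality handling.

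**The concern.** Safety and tolerability of peposertib in combination is a secondary objective, and peposertib is the investigational drug. The component tables are where the SAP separates its contribution from that of RT and capecitabine. In those tables the rule as written can only lower the counts, whereas the pooled row takes the cautious side.

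The pooled row also stops being the union of its parts. SAP 15.2.1 labels it as covering peposertib, RT or capecitabine, so a reader would expect every event in it to appear in at least one component row. An event with missing causality need not.

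The listings would not show the difference. The planned component flags in SAP 15.2.1 take only the values N and Y, so a missing relationship cannot be told from an unrelated one. By contrast, the tables by worst grade say explicitly that events with a missing grade are included under any grade.

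**Working it through.** There is no figure in the plan to reproduce. The check is to apply the rules as written to the possible causality patterns, then to size the effect on a participant-level percentage.

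**Step 1: apply the SAP rules.** The pooled definition is read as satisfied when at least one relationship is missing, unknown or related. The component definitions are applied with the Section 9 default of no replacement. Unknown behaves like missing throughout.

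| Peposertib | RT | Capecitabine | Pooled row | Peposertib row | RT row | Capecitabine row |
|---|---|---|---|---|---|---|
| related | unrelated | unrelated | yes | yes | no | no |
| missing | missing | missing | yes | no | no | no |
| missing | unrelated | unrelated | yes | no | no | no |
| missing | related | unrelated | yes | no | yes | no |

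In the second and third patterns the event is related to trial treatment but to no component. In the fourth it is credited to RT alone. If missing were counted as related for each component, the peposertib row would read yes in all four patterns.

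**Step 2: size.** The tables count participants, so a participant is lost from a row only if every event that could place them in it has missing or unknown peposertib causality. Let k be the number of such participants and n the denominator. The percentage falls by 100 × k/n.

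Inputs:

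- n = 3, the planned cohort size (protocol Section 9.2).
- n = 6, if a dose level receives the up to 3 further participants that protocol Section 4.1.2 allows in exceptional cases: 3 + 3.
- n = 19, the participants treated as of 06 May 2021 (protocol synopsis).
- k is not given in the documents. It is assumed to lie between 0 and 3 overall.

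Results:

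| k | n | Fall in peposertib-related percentage |
|---|---|---|
| 0 | any | 0 points |
| 1 | 3 | 1/3 = 33.3 points |
| 1 | 6 | 1/6 = 16.7 points |
| 1 | 19 | 1/19 = 5.3 points |
| 2 | 19 | 2/19 = 10.5 points |
| 3 | 19 | 3/19 = 15.8 points |

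The pooled percentage does not change in any of these cases. In the table limited to terms seen in at least 2 participants, a term with exactly 2 would disappear if one were lost.

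**Step 3: the primary endpoint.** SAP 15.1 takes dose limiting toxicities from dedicated eCRF items, and the summary counts those decided by the Safety Monitoring Committee. The causality counting rule does not enter.

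**The case against.** The strongest reply is that the SAP follows the protocol. The missing-data sentence in Table 13 comes directly after an aggregate definition and can be read as extending that definition only. Every related-event summary that Table 13 plans is for the study intervention as a whole, and the SAP applies the missing rule to all of them and widens it to unknown. The component tables are additions by the SAP, and the protocol has no component definition for them to breach. This stands. A reader might infer that the SAP contradicts the protocol, but the documents do not support that: the optional plural in the protocol sentence allows a reading per intervention without requiring it, and the SAP is silent on the components rather than stating an opposite rule.

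The second reply is that missing causality should be rare. Protocol Appendix 7 requires a systematic assessment as related or unrelated and asks for the causal relationship in each event report, and Appendix 2 places database lock after quality control. This also stands, and it limits the likely size. It does not remove the gap, because the SAP itself provides for missing and unknown values in the pooled row. Appendix 7 also requires a reasonable alternative explanation before an event is called unrelated; a blank field offers none, yet the component tables would treat it as unrelated.

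Third, the affected events stay visible in the overall, serious, Grade 3 or higher and pooled-related tables and in the listing of all events. That is true. What is at risk is attribution to the component, not detection of the event.

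Fourth, counting a blank as related to each component blurs the attribution that these tables are meant to show. That is a real cost, and the footnote proposed below is there to make it visible.

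**Conclusion.** The point holds as a gap in SAP 15.2, and it is minor. The missing-counts-as-related rule reaches only the pooled category. With the Section 9 default, missing or unknown causality for a component takes the event out of that component's related tables, so an event can be related overall but to none of its components.

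The consequence is that peposertib-related events can be under-counted. It would be too strong to say that they are: no missing or unknown entries are documented, and with complete causality data the effect is zero. The figures of 33 points in a dose level of 3 and 5 points among 19 are worst cases for one participant with no other qualifying event in that row. They assume that a level stayed at 3 and that 19 remains the denominator.

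A reader might also infer a risk to the dose-finding result. The documents do not support that, since the dose limiting toxicity endpoint does not use this rule.

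**What to change.** In SAP 15.2, define events related to peposertib as those whose relationship to peposertib is recorded as related, missing or unknown, and do the same for RT and for capecitabine. Footnote each component table with the number of events counted only because causality was missing or unknown, so that readers can take them out again.

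The cost is one reworded sentence and a footnote. Component counts may be slightly higher and attribution slightly less specific, for example when an event recorded as RT-related has a blank for peposertib. If all causality entries are complete, nothing changes and the footnote reads zero.
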